9.2 Secondary Objectives

1) To compare the time from sample acquisition to receipt of result (turnaround time) for Logicore System point of care testing and current POC testing (Cepheid multiplex GeneXpert)

- 2) To evaluate the acceptability of the Logicore System device by study participants and staff.
- 3) To produce targeted Cost Benefit analysis for the Logicore System device.

10.0 STUDY ENDPOINTS

10.1 Primary Endpoint / Outcome Measure

The primary endpoint of the study is to measure the sensitivity and accuracy of Logicore System POC diagnostic test compared to gold standard POC multiplex test (Cepheid GeneXpert), including PPV, NPV and specificity.

10.2 Secondary Endpoint / Outcome Measures

- 1) Determination of turnaround time for Logicore System and Cepheid tests (time taken from nasopharyngeal swabbing procedure to receipt of positive result).
- 2) Evaluation of acceptability of Logicore System POCT to study participants and staff.
- 3) Targeted Cost Benefit analysis of Logicore System POCT.

11.0 STUDY DESIGN

This is a prospective, single-centre, diagnostic accuracy study, being conducted at Addenbrooke's Hospital in Cambridge. Participants can be any age but must exhibit acute respiratory symptoms on presentation at the Emergency Department and require standard of care diagnostic testing as per CUH Trust IPC policy.

The study will be performed in accordance with the Declaration of Helsinki⁵, principles of Good Clinical Practice⁶ and local and regulatory requirements.

The study is aiming to recruit 400 participants. There is no Investigational Medicinal Product involved and therefore no treatment arms and no randomisation. Swab samples taken from each participant will be tested by standard POCT (control data) and by Logicore System POCT device.

Members of the research ream will utilise Personal Protective Equipment (PPE) in line with the CUH Infection Prevention and Control Guideline.

There is only one visit required for each participant, during which the following data will be collected:

- Study identifying number
- Date of Visit and Study Assessments (presentation at ED)
- Sex
- Age in years
- Emergency Care Data Set (ECDS) presentation code
- Clinical signs and symptoms of respiratory tract infection
- Date of onset of clinical symptoms of respiratory tract infection
- Time nasopharyngeal swabs taken
- Time results available from Cepheid and Logicore System devices (to establish turnaround time in minutes)
- Hospital admission required? Y/N
- Intensive care admission required? Y/N
- NEWS-2 Score for participants 15 years of age and above
- PEWS (Paediatric Early Warning Score) for participants less than 15 years of age
- Arrival by ambulance? Y/N
- Respiratory rate (breaths per minute)
- Temperature (in °C)
- Heart rate (beats per minute)
- Blood pressure (systolic and diastolic)
- Oxygen saturation (%)
- Confirmation that Logicore System Instructions For Use (IFU) were followed to test the sample using the new device
- Participant and staff assessment of acceptability
- Adverse event details.

Following discharge from the ED (to home, nursing home or a hospital ward etc), the following additional information will be collected:

- 7, 14 and 30-day mortality
- Discharge diagnosis confirmation.

To assess the acceptability of the testing process, each participant will be asked the following question:

'How unpleasant was the swab'?

The participants must rate the swabbing process according to the following categories:

- 1) Very unpleasant
- 2) Slightly unpleasant

- 3) I didn't mind
- 4) I really didn't mind.

Thus, the greater the aggregated score for all participants, the more acceptable the swab process was felt to be.

Each participant will also be asked a second question as follows:

'If you had to have the swab done again, how would you feel about it'?

The participants must give an answer from the following responses:

- 1) Happy
- 2) I wouldn't mind
- 3) Unhappy.

To assess the acceptability of using the Logicore System, ED research team staff will be asked the following question:

'How difficult was the Logicore System to use'?

The staff must rate the Logicore System process according to the following categories:

[figure not shown]
- 1) Very difficult
- 2) Slightly difficult
- 3) Quite easy
- 4) Very easy.

Thus, the greater the aggregated score for all staff, the more acceptable the Logicore System was felt to be.

The study duration will be a one-off face-to-face visit for participants. The Research Nurse or designated member of the ED research team will use the hospital electronic patient record system to obtain the required post-discharge details. Participants will be considered as in the study from the date of signed informed consent form until the date of discharge from the ED. As there is no additional hospital visit required for the study, there is no provision for participant's travel or sustenance expenses, and participants will not be paid to take part in the study.

Figure 1: Sample Collection and Testing Process

If Cepheid and Logicore System results are both positive for the same pathogen, or both negative for all pathogens then the results will simply be recorded.

A. If the Cepheid result is positive but the Logicore System result is negative, the Logicore System test will be classed as a false negative.

B. If the Cepheid and Logicore System results are positive for different pathogens, it is not possible to test the participant again as the result from the gold standard Cepheid test will be taken as correct and used to determine appropriate treatment. The participant would not have repeat testing according to standard care. If the Logicore System result is positive for one of the pathogens that Cepheid does not test for (i.e. *Mycoplasma pneumoniae* or human adenovirus), it will be taken to be a true positive result. If however, the Logicore System result is positive for a different pathogen that Cepheid does test for (i.e. Flu A, Flu B, RSV or SARS-CoV-2) but it is not the same pathogen that is positive according to the Cepheid result, the Logicore System result will be classed as a false positive.

C. If the Cepheid result is negative but the Logicore System result is positive, and the participant still exhibits clinical symptoms of respiratory infection requiring diagnostic testing as per CUH Trust Infection Prevention and Control Guideline, a second single swab will be taken from the participant and used for second-line testing as per the CUH Trust standard UK HSA laboratory respiratory virus PCR testing policy. The result from the second-line testing will then be compared to the initial Logicore System result. If the Logicore System result agrees with the second-line result, it will be classed as a true positive. If it does not match the pathogen from the second-line testing, the initial Logicore System result will be classed as a false positive.

The current gold standard POCT at CUH is Cepheid and the second-line PCR test is Luminex, as specified in their IPC Guideline. However, it must be noted that this study is taking place in a real-world setting which may be subject to change due to NHS supply issues, purchasing changes or other factors outside the control of the ED research team. This has been considered during the design of this protocol. If the second-line testing device happens to change during the course of recruiting participants into this study, the replacement second-line device will still need to test for the 2 additional pathogens that the Logicore System tests for. If the second-line testing device changes during the study, the sample collection and testing process shown in Figure 1 will not change. Thus, the Logicore System results will always be compared to the CUH gold standard POCT and when required, to the standard of care second-line testing device that is being used to identify infectious cases in the ED.

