5.0 PROTOCOL SYNOPSIS

C4d C	
Study Summary	
Protocol Title	Evaluation of Digital Microfluidic Molecular Point Of Care Testing for Respiratory Pathogens Diagnosis
Short Title	Study for Multiplex Assessment and Respiratory Test evaluation; SMART
Study Objectives	To evaluate the analytical performance, turnaround time, operability and acceptability of a novel multiplex respiratory pathogens point of care test device compared to currently available point of care testing.
Study Procedures	Participants will be swabbed to provide samples which will be analysed by standard testing and by the novel multiplex device. The procedures will take place in a single visit in the Emergency Department at Addenbrooke's Hospital in Cambridge. Additional relevant data will be collected from the participants' hospital medical records. No further participant involvement is required.
Study Sponsor	Logilet (UK) Ltd
Sponsor	[name] ([name])
Representative	Product Manager
Study Design	This is a prospective, single centre, single visit, diagnostic performance study. There is no therapeutic agent involved and therefore no randomisation into treatment arms. Two nasopharyngeal swabs will be taken simultaneously from each participant (one from either nostril) and used for Point Of Care Testing using the current gold standard and novel in vitro diagnostic devices. In this way, participants will act as their own controls for comparison of results. If the initial standard test is negative but the participant continues to exhibit clinical symptoms of respiratory infection, a further swab may be taken and tested as per Cambridge University Hospitals NHS Foundation Trust (CUH) policy with another standard device.
Investigational Medical Device	The Logicore System in vitro diagnostic device utilises digital microfluidics to rapidly test for the presence of 6 respiratory pathogens, namely SARS-CoV-2, Influenza A (FluA), Influenza

	Ţ
	B (FluB), Respiratory Syncytial Virus (RSV), Mycoplasma pneumoniae (MP) and human adenovirus (HAdV). The Logicore System produces results in approximately 63 minutes and is expected to feature improved sensitivity when compared to the current gold standard testing device.
Study Location	Cambridge University Hospitals NHS Foundation Trust (CUH)
	Emergency Department
	Addenbrooke's Hospital Cambridge Biomedical Campus
	[name]
	Cambridge
	[name]
Study Duration	When the sample size has been reached, or a maximum of four

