13.5.4 Participant Follow Up

Participants enrolled into the study will be considered to have completed their participation in the study once all the required swabs have been tested and results obtained. (This may simply be one set of 2 swabs, or one set of 2 swabs for initial Logicore System and Cepheid testing plus an additional single swab for second-line testing, if the initial Cepheid result was negative but the participant continues to exhibit clinical symptoms of respiratory infection and needs to be tested as per Trust IPC guideline). Any positive results will be communicated to the participant's medical care team and documented in their electronic medical records. No follow up is required for the study. Participants will continue to receive appropriate medical care outwith the study. This study has no bearing on the clinical management of the participants.

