20.0 APPENDICES

20.1 Appendix 1 – Details of Equipment Used in the Study

The gold standard in vitro diagnostic device used at CUH, is Cepheid POCT (GeneXpert).

Following a negative Cepheid result, if a patient still exhibits clinical symptoms of respiratory infection, the standard second-line testing device is Luminex NxTag, as per CUH Trust Infection Prevention and Control Guideline at the time of devising this protocol.

The IVDD that is the subject of this investigation is the Logicore System.

The Logicore POCT System will always be assessed against the gold standard first-line POCT and standard of care second-line testing devices in line with the Trust IPC policy.

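### For Flu A, Flu B and RSV, a Logicore-only positive confirmed by second-line PCR is a true positive under section 11.0 rule C but a false positive in the Cepheid-only 2x2 tables, and using the rule C label can only favour Logicore

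*Protocol*

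**What the plan says.** Section 11.0 of the Protocol gives the classification rules under Figure 1. (The flowchart is not visible in the text reviewed, so this point rests on the written rules.)

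- Concordant results: when the tests are "both negative for all pathogens then the results will simply be recorded". No rule can turn such a case into a Logicore miss.
- Rule A: Cepheid positive with Logicore negative is a Logicore false negative, with no further test.
- Rule C: "If the Cepheid result is negative but the Logicore System result is positive, and the participant still exhibits clinical symptoms of respiratory infection", a second swab goes to second-line PCR. "If the Logicore System result agrees with the second-line result, it will be classed as a true positive"; a mismatch is a false positive.

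The statistical sections take a different standard. Section 14.1 bases the plan on Logicore against Cepheid and declines a composite reference. Section 14.2.1 defines the primary endpoint against Cepheid for the four overlapping infections. Section 14.5.1 builds one 2x2 table per disease against the paired standard, with test-positive/standard-negative as the false-positive cell. Section 14.6 takes specificity in patients negative on the gold standard.

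Two places keep the second-line device in the comparison. The last paragraph of section 11.0 adds it when required, and Appendix 1 states that "The Logicore POCT System will always be assessed against the gold standard first-line POCT and standard of care second-line testing devices".

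**The concern.** The same confirmed result carries two labels in one document, and the label decides which cell it enters. The second-line test can overturn a Cepheid negative only in Logicore's favour: it is consulted for classification when Logicore is positive and never when Logicore is negative. This is one-sided discrepant resolution. It touches sensitivity, specificity and PPV, all of which belong to the primary endpoint in section 10.1, while the primary objective in section 9.1 is increased sensitivity. If the label is chosen after results are seen, the reported accuracy depends on that choice.

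**Working it through.** **Same result, two labels.** Take a symptomatic participant who is RSV-negative on Cepheid, RSV-positive on Logicore and RSV-positive on second-line PCR. Section 11.0 rule C makes this a true positive. Section 14.5.1, with Cepheid as the standard, makes it a false positive.

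**Direction.** Let TP, FP, FN and TN be the Cepheid-only cells for one pathogen, and k the number of Logicore-only results that second-line PCR confirms. Rule C moves k results from FP to TP. Nothing else moves: mismatches stay FP, FN is fixed by rule A, and double negatives stay TN. A second-line result for a different panel pathogen would reveal a Logicore miss, but rule C labels it only a false positive.

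- Sensitivity: TP/(TP+FN) becomes (TP+k)/(TP+k+FN). The change is k·FN/[(TP+FN)(TP+FN+k)], which is never negative and is zero if k = 0 or FN = 0.
- Specificity: TN/(TN+FP) becomes TN/(TN+FP−k), never lower.
- PPV: TP/(TP+FP) becomes (TP+k)/(TP+FP), never lower.
- NPV: TN/(TN+FN) does not change.

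**The plan's own figures.** Section 14.3.1: 1.96² × 0.95 × 0.05 / 0.10² = 18.25, rounded up to 19; 19/0.05 = 380; 380 + 20 = 400. These reproduce. At the lowest prevalence (Flu B, 5%), 400 participants give 20 positives.

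**Illustration for Flu B.** Assumed, because the Protocol gives no such counts: 20 Cepheid positives split 19 TP and 1 FN, and 8 Logicore-only results among the 380 Cepheid negatives (TN = 372).

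| k confirmed | Sensitivity | Specificity | PPV |
|---|---|---|---|
| 0 (Cepheid only) | 19/20 = 95.0% | 372/380 = 97.9% | 19/27 = 70.4% |
| 4 | 23/24 = 95.8% | 372/376 = 98.9% | 23/27 = 85.2% |
| 8 | 27/28 = 96.4% | 372/372 = 100% | 27/27 = 100% |

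The k = 8 row is an extreme. It implies that Cepheid found 20 of 28 infections (71%), below the range used next.

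**Size under a model.** Assume independent errors, no false positives, a perfect second-line test and every rule C case tested. Write sL and sC for the true sensitivities of Logicore and Cepheid. The Cepheid-only table then gives sL, and rule C gives sL/[sL + sC(1 − sL)].

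| sL | sC | Rule C | Shift (points) |
|---|---|---|---|
| 0.95 | 0.95 | 0.95/0.9975 = 95.24% | 0.24 |
| 0.95 | 0.80 | 0.95/0.99 = 95.96% | 0.96 |
| 0.80 | 0.95 | 0.80/0.99 = 80.81% | 0.81 |
| 0.80 | 0.80 | 0.80/0.96 = 83.33% | 3.33 |

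Per 20 infections, Logicore-only detections number 20(1 − sC)sL = 0.8 to 3.8, and infections missed by both number 20(1 − sL)(1 − sC) = 0.05 to 0.8.

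**Shared misses.** Let m be the share missed by both tests. Rule C gives sL/(1 − m); Cepheid-only gives (sL + sC − (1 − m))/sC. At 80%/80% with m = 0.10 these are 88.9% and 87.5%, a shift of 1.4 points. With m = 0.20 both are 100% and the shift is 0.

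**Pathogens affected.** The Luminex panel listed in section 7.1 does not name SARS-CoV-2. As listed, k = 0 for that pathogen, which leaves Flu A, Flu B and RSV.

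**The case against.** The strongest reply is that the planned test of superiority is not touched. Section 14.5.1 judges superior sensitivity by McNemar's test on raw paired positives and negatives, and no rule C label enters it. That stands. A reader might infer that rule C biases the test of the primary objective; the Protocol does not support this.

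A reader might also infer that confirmed Logicore-only detections say nothing about sensitivity. That goes too far. With rule C labels, Logicore detects TP + k and Cepheid TP + FN over the same denominator, so the comparison is k against FN and infections missed by both tests cancel. Nor do the rules as a whole demonstrably favour Logicore: rule A has no resolver, so every Cepheid false positive that Logicore does not share counts against Logicore. The direction shown here holds only relative to the Cepheid-only table.

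The Cepheid-only table is no unbiased measure either. In the shared-miss example true sensitivity is 80%, yet that table gives 87.5% against 88.9% for rule C. This stands, and it is why the fix calls the result agreement with Cepheid.

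Sections 14.1, 14.2.1, 14.5.1 and 14.6 do point consistently to Cepheid. But section 11.0 and Appendix 1 say otherwise, and nothing ranks one over the other.

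Finally, a reader might see a second contradiction in who is swabbed. The synopsis says "If the initial standard test is negative but the participant continues to exhibit clinical symptoms of respiratory infection, a further swab may be taken", and section 13.5.4 and Appendix 1 likewise set no Logicore condition. But the synopsis wording is permissive, the footnote to section 13.5.1 makes the extra swab depend on the initial results, and rule C does not forbid routine testing of double negatives. The difference changes no 2x2 cell and is a matter of wording only.

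**Conclusion.** The inconsistency is real for Flu A, Flu B and RSV, and its direction is certain: relative to the Cepheid-only table, rule C labels never lower Logicore's sensitivity, specificity or PPV. The sensitivity effect is small at planning values, at most about 1 point against a planned precision of 10 points. The 3.3-point figure needs both tests at 80%, which the Protocol does not suggest. PPV can move much further, but by how much depends on counts the Protocol does not give. The sizes rest on the assumptions stated with the model and shrink if misses are shared. What needs correcting is an unsettled, one-sided label in the primary accuracy tables; the McNemar comparison is sound on this point. For *Mycoplasma pneumoniae* and adenovirus, which Cepheid does not test, rule C conflicts with nothing in the primary endpoint.

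**What to change.** 1. State in sections 11.0 and 14.5.1 that the primary 2x2 tables for the four shared pathogens use Cepheid alone, and that the rule C true-positive label does not enter them. This also settles Logicore-only positives whose symptoms have resolved, for whom rule C gives no label.
2. Describe those results as agreement with Cepheid. Cepheid scores 100% against itself by definition, so TP/(TP+FN) cannot show Logicore to be more sensitive. Align the sensitivity-difference entry in section 14.6 accordingly.
3. Report second-line results separately and descriptively. Give confirmed Logicore-only counts beside Cepheid-only counts, plus any second-line positives found in double negatives under Trust policy, and note that verification under rule C was conditional on a Logicore positive.
4. Keep rule C for *Mycoplasma pneumoniae* and adenovirus.
5. Optionally, use one wording for the extra-swab trigger. Which trigger is clinically right is for the investigator and the Trust.

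Cost: Protocol wording and one eCRF field for the second-line result. No added participants and no added tests.

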The CUH IPC Guideline² states all symptomatic patients who are to be admitted from ED must have Cepheid monoplex POCT PCR assay performed to test for SARS-CoV-2. During the winter months when there is a high prevalence of seasonal respiratory viruses, a Cepheid multiplex POCT PCR assay is utilised instead which tests for influenza A, influenza B, Respiratory Syncytial Virus (RSV) and SARS-CoV-2. Hospital inpatients who did not exhibit respiratory symptoms at admission but go on to develop them are tested using a SARS-CoV-2 POCT PCR (SAMBA) test and also UK HSA laboratory respiratory PCR swab Luminex analysis which tests for human adenovirus, seasonal coronaviruses, human bocavirus, human metapneumovirus, influenza A (H1, H3, 2009 H1N1), influenza B, parainfluenza (1-4), picornaviruses (rhino/ enterovirus), RSV A and B, *Chlamydia pneumoniae*, *Legionella pneumophila* and *Mycoplasma pneumoniae*. Patients who are admitted to hospital after testing negative on the Cepheid POCT in the ED but with ongoing clinical concern for respiratory viral infection, may also undergo additional UK HSA laboratory respiratory virus PCR testing.

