13.5 Schedule of Events

13.5.1 Per Participant Activities

Activity	At ED Visit
Review of PIS and signing of ICF/Assent form	Х
Signs and symptoms of acute respiratory tract infection	Х
Temperature	Х
Heart rate, respiratory rate, blood pressure and oxygen saturation	Х
Nasopharyngeal swabs x2 (simultaneously taken) for initial testing by standard Cepheid device and novel Logicore System device	Х
Additional nasopharyngeal swab for testing by second-line device*	Х
Assessment of acceptability (Likert-scale)	Х
Adverse event details	Х

^{*}Additional nasopharyngeal swab may or may not be required, depending on the results from the initial testing and depending on the clinical status of the participant according to Trust IPC policy.

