14.3.4 Cost Effectiveness Analysis

We will be using real patient data on those who fail the original test but are positive on the new test device and have ongoing symptoms requiring further hospital activity and

testing. Potentially some may spontaneously improve after the first test and be lost to this analysis.

The data may consist of individual measures of Length Of Stay (LOS), complications, time to treatment etc.

$$n = \left(rac{(Z_{1-lpha/2} + Z_{1-eta}) \cdot \sigma}{\Delta}
ight)^2$$

The sample size depends on:

 σ = the SD of the effect or costs

 Δ = minimally important clinical difference.

For example: cost saving £500 with an SD of £1000 then n = 31.4 or a requirement of 32 per group to analyse.

If we argue that a maximum of 5% of cases will fail the standard test but be positive on the new test and reflex test, then at around 400 patients total we should hope to see 20 - 25 patients per extra infection which is enough to evaluate impact meaningfully.

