14.5 Statistical Methods

14.5.1 Primary Outcomes

The outcome data from each testing device will be compared against its paired standard to produce 2 x 2 tables for each type of disease

Disease +ve Disease -ve

	Standard positive	Standard negative
Test positive	True Positive (TP)	False Positive (FP)
Test negative	False Negative (FN)	True Negative (TN)

From this we calculate:

i. Sensitivity, Specificity

Sensitivity is the percentage of cases that had the observed outcome was correctly predicted by the model (i.e., TP/(TP+FN).

Specificity is the percentage of observations that were also correctly predicted as not having the observed outcome (i.e., TN/FP+TN).

- ii. Positive Predictive Value
- iii. Negative Predictive Value
- iv. Likelihood Ratios (LR+ / LR-) for the strength of the test versus standard
- v. Accuracy and Cohen Kappa (for agreement)
- vi. If data allows, we intend to model some ROC curves around the various clinical thresholds to ascertain the best use model for this device in this clinical setting.

These core calculations and tests will be performed using JASP software on the recorded data sets.

vii. McNemar's test to compare sensitivity/ specificity.

McNemar's test will be used to assess paired differences in positive and negative results between the new POCT and the established gold standard test for each of the four shared respiratory infections. This test focuses on cases where the two tests disagree, quantifying whether the new test detects significantly more or fewer positive results than the comparator.

For example, among patients tested for RSV, if the new test identifies more positive cases than the gold standard, and this difference is statistically significant on McNemar's test (p < 0.05), this may indicate **superior sensitivity**. Results will be reported with the test statistic, degrees of freedom, and p-value. A similar analysis will be repeated for each infection, supporting the primary endpoint of diagnostic accuracy.

McNemar tests the **null hypothesis** that both tests have the same proportion of positive results by evaluating a test statistic and comparing this with a Chi squared distribution statistic if the value is lower then the null hypothesis is proved.

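### Rule C and the 14.5.1 table label the same Logicore-only positive differently, and rule C gives no label when no second-line swab is taken, so adjudicated PPV and specificity depend on who is clinically re-tested

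*Protocol*

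**What the plan says.** Section 11.0 sets out how pairs of results are classed. Concordant pairs are recorded, rule A covers Cepheid-positive/Logicore-negative pairs, and rule B covers pairs positive for different pathogens. Rule C covers Cepheid-negative/Logicore-positive pairs and adds the condition "and the participant still exhibits clinical symptoms of respiratory infection requiring diagnostic testing as per CUH Trust Infection Prevention and Control Guideline". If that is met, a second swab goes to second-line testing and two outcomes follow: "If the Logicore System result agrees with the second-line result, it will be classed as a true positive", and "If it does not match the pathogen from the second-line testing, the initial Logicore System result will be classed as a false positive". The text has no branch for a pair where the condition is not met or no second-line result exists.

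Other sections confirm that the swab is not universal. Section 13.5.1 states: "Additional nasopharyngeal swab may or may not be required, depending on the results from the initial testing and depending on the clinical status". Section 7.1 says that patients admitted after a negative Cepheid test with continuing concern "may also undergo additional UK HSA laboratory respiratory virus PCR testing".

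Section 14.5.1 compares each device with its paired standard to "produce 2 x 2 tables for each type of disease". In that table every test-positive/standard-negative result is a false positive. Neither rule C nor the second-line result is mentioned.

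**The concern.** The two sections cannot both govern the same cell. Under rule C a Logicore-only positive that second-line testing confirms is a true positive; under 14.5.1 it is a false positive. One that is not re-tested is a false positive under 14.5.1 and has no stated label under rule C.

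If any form of adjudication is used, this is partial verification: the reference result exists only for patients whose symptoms and Trust policy led to a second swab. Section 10.1 names PPV and specificity within the primary endpoint. Logicore-only positives are also the sole source of false positives among patients negative on all Cepheid targets. How the unverified ones are handled therefore moves both measures, and the protocol does not fix one way of doing it.

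**Working it through.** **Plan figures.** The protocol gives no figure for this point. Its sample-size figures reproduce: 1.96² × 0.95 × 0.05 / 0.10² = 18.25, rounded up to 19; 19/0.05 = 380; 19/0.15 = 127. They are not in dispute.

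**The labels side by side, for a Cepheid-negative, Logicore RSV-positive pair**

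- Re-tested, second-line RSV positive: true positive under rule C, false positive under 14.5.1.
- Re-tested, second-line RSV negative: false positive under both.
- Not re-tested: no stated label under rule C, false positive under 14.5.1.

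**Inputs.** From the protocol: 400 participants, RSV prevalence 15% (14.1), expected sensitivity 95% (14.2.1). Assumed, because the protocol gives no values: 10 Logicore-only RSV positives, 5 re-tested, 80% of re-tested ones confirmed.

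**Counts.** Cepheid positive: 400 × 0.15 = 60. Concordant positive: 0.95 × 60 = 57. FN: 60 − 57 = 3. TN: 400 − 60 − 10 = 330. Of the 5 re-tested, 4 are confirmed and 1 is not, leaving 5 unverified.

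PPV = TP/(TP+FP); specificity = TN/(TN+FP); sensitivity = TP/(TP+FN).

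| Handling | TP | FP | FN | TN | PPV | Specificity | Sensitivity |
|---|---|---|---|---|---|---|---|
| Unverified dropped | 61 | 1 | 3 | 330 | 61/62 = 98.4% | 330/331 = 99.7% | 61/64 = 95.3% |
| Unverified all FP | 61 | 6 | 3 | 330 | 61/67 = 91.0% | 330/336 = 98.2% | 61/64 = 95.3% |
| Unverified all TP | 66 | 1 | 3 | 330 | 66/67 = 98.5% | 330/331 = 99.7% | 66/69 = 95.7% |
| All 10 verified, 80% confirmed | 65 | 2 | 3 | 330 | 65/67 = 97.0% | 330/332 = 99.4% | 65/68 = 95.6% |
| Cepheid only | 57 | 10 | 3 | 330 | 57/67 = 85.1% | 330/340 = 97.1% | 57/60 = 95.0% |

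**Direction.** Against full verification, dropping the unverified raises PPV by 98.4 − 97.0 = 1.4 points and specificity by 99.7 − 99.4 = 0.3 points when re-testing is unrelated to truth. Defaulting them to FP lowers PPV by 97.0 − 91.0 = 6.0 points and specificity by 99.4 − 98.2 = 1.2 points, because unverified true infections are charged as errors.

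**Range over the share re-tested.** With 3 of 10 re-tested (2 confirmed), PPV is 59/60 = 98.3% if dropped and 59/67 = 88.1% if counted FP. With 8 of 10 re-tested (6 confirmed), it is 63/65 = 96.9% and 63/67 = 94.0%. The gap between the two labels runs from about 10 points to about 3.

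**Selective re-testing.** As a panel-level illustration, take 30% Cepheid positivity (lower end of the range in 14.1): 120 positive, 0.95 × 120 = 114 concordant, 280 Cepheid negative. Assume 20 Logicore-only positives, 10 real and 10 spurious, with 8 of the real and 2 of the spurious re-tested; TN = 280 − 20 = 260. With the unverified dropped, PPV is 122/124 = 98.4% and specificity 260/262 = 99.2%. The true values are 124/134 = 92.5% and 260/270 = 96.3%. The upward bias is then 5.9 and 2.9 points.

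**The case against.** A reader might infer that unverified positives vanish, so that the primary PPV and specificity are computed on a selected subset. The documents do not support that. No section says these pairs are dropped, and 14.5.1 does give them a label. Section 14.1 bases the plan on validation against Cepheid rather than a composite reference, and the 14.6 specificity row is defined in gold-standard negatives. A natural reading is that false positive against Cepheid is the default and rule C overrides it where a second-line result exists. Selection also touches only the Logicore-only positives; concordant pairs and rules A and B do not wait on a second swab.

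The number unverified may be small. Section 7.1 ties first-line ED testing to patients who are to be admitted, and inclusion criterion 6 requires testing under Trust policy. The remark in 14.3.4, "Potentially some may spontaneously improve after the first test and be lost to this analysis", concerns the cost analysis only and is not evidence about accuracy labelling. Section 14.6 lists specificity, PPV and NPV under secondary rows, although 10.1 places them in the primary endpoint. The Figure 1 drawing is not available here, so the missing branch is judged from the written rules.

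It is also tempting to read the 98.4% against 91.0% contrast as the bias. It is the distance between two labels; the upward bias from dropping is 1.4 points if re-testing is unrelated to truth.

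All of this limits the size. It does not remove the conflict. The default-and-override reading is itself biased downward, because only re-tested patients can escape the false-positive label. Only a purely Cepheid-based table avoids the problem, and rule C would then play no part in it, which the protocol does not say.

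**Conclusion.** The point holds as a conflict between section 11.0 and section 14.5.1, together with partial verification in any analysis that uses second-line results. Rule C fixes no label for a Logicore-only positive without a second-line result, and the table disagrees with rule C for those that are confirmed.

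Dropping the unverified can only leave specificity unchanged or raise it, since TN stay and only FP can be lost. It raises PPV when re-testing is unrelated to truth or favours real infections. Defaulting to FP with override only for the re-tested lowers both measures whenever any unverified positive is real.

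The magnitude cannot be derived from the documents: the numbers of Logicore-only positives, re-tests and confirmations are all assumed. In the RSV illustration the handling matters by several points for PPV and by under 2 points for specificity; selective re-testing could widen this. It is not established that the planned primary result rests on a verified subset.

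**What to change.** Reconcile rule C in section 11.0 with section 14.5.1.

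1. Make the per-pathogen table against Cepheid alone the main analysis. Every Cepheid-negative/Logicore-positive pair goes in the test-positive/standard-negative cell, re-tested or not.
2. Report the second-line-adjudicated analysis separately. Give the number of unverified Logicore-only positives per pathogen, and show bounds by recomputing the whole 2x2 table twice: once with all unverified as FP, once with all as TP. In the second table they leave the specificity denominator (FP+TN) and enter TP+FN, so sensitivity is recomputed too.
3. Do not report PPV or specificity from the verified subset alone.

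This costs a few sentences in the two sections and one extra row per pathogen table. No extra swab and no change to care are needed. The downside is presentational: the Cepheid-only table charges confirmed extra detections as false positives (85.1% PPV in the RSV illustration), and the adjudicated values appear as a range (91.0% to 98.5%) that looks less favourable than a single figure. The bounds address unverified Logicore-only positives only; pairs negative on both devices are not adjudicated under section 11.0 either.
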